7.18 Sleep Questionnaire: Children’s Sleep Habits Rating Scale

A sleep questionnaire, Children’s Sleep Habits Rating Scale, will be administered to the patient's patients/legal guardian.

7.19 Age-Dependent, Health-Related Quality of Life in Children

The Quality of Life questionnaires will be administered as outlined in Sections 7.19.1, 7.19.2, and 7.19.3.

7.19.1 Quality of Life Indicator: CHQ-50

The Child Health Questionnaire™ Parent Form 50 Questions (CHQ-50) will be administered during the study.

The questionnaire is a generic quality of life instrument, measuring 14 unique physical and psychosocial concepts, which was developed for children from 5 to 18 years of age

7.19.2 Quality of Life Indicator: CHQ-87

The Child Health Questionnaire™ Child Form 87 (CHQ-87) will be administered during the study. The CHQ-87 is a child and adolescent self-report, developed for ages 10 and older, which assesses the child's self-perceived physical and psychosocial well-being

7.19.3 Quality of Life Indicator: ITQOL

The Infant Toddler Quality of Life Questionnaire™ (ITQOL) will be administered during the study. The ITQOL was developed for children at least 2 months of age up to 5 years and assesses the physical, mental, and social well being of the child and assesses the quality of the parent/guardian's life.

7.20 Concomitant Medications, Therapies and Medical/Surgical Procedures

All non-protocol treatments that occur from the time of informed consent (assent if applicable) through the safety follow-up contact are regarded as concomitant and will be documented on the appropriate pages of the eCRF. Concomitant therapy includes medication, therapies/interventions administered to patients, and medical/surgical procedures performed on the patients.

Every effort should be made to keep symptomatic Sanfilippo syndrome Type A treatment constant throughout the study. However, changes in medications are acceptable if necessary according to clinical judgment. All changes will be recorded on the appropriate eCRF. Concomitant medication will be coded using WHODRL.

7.21 Adverse Events

7.21.1 Adverse Events Assessments

Adverse events will be monitored continuously throughout the study from the time the patient, patient's parent/legal guardian signs the informed consent/assent (if applicable) until the safety follow-up contact or until the event has resolved or stabilized, or an outcome is reached, whichever comes first.

If the Investigator considers it necessary to report an AE in a study patient after the end of the observation period, he or she should contact the Sponsor to determine how the AE should be documented and reported.

7.21.2 Definitions of Adverse Events and Serious Adverse Events

7.21.2.1 Adverse Event

An adverse event (AE) is any noxious, pathologic, or unintended change in anatomical, physiologic, or metabolic function as indicated by physical signs, symptoms, or laboratory changes occurring in any phase of a clinical study, whether or not considered study drug-related. This includes an exacerbation of a pre-existing condition. Once the informed consent is signed, any adverse event prior to the start of study drug must be reported.

AEs include:

- Worsening (change in nature, severity, or frequency) of conditions present at the onset of the study
- Intercurrent illnesses
- Drug interactions
- Events related to or possibly related to concomitant medications
- Abnormal laboratory values (this includes significant shifts from baseline within the range of normal that the Investigator considers to be clinically important)
- Clinically significant abnormalities in physical examination, vital signs, and weight

Throughout the study, the Investigator must record all AEs on the AE case report form (eCRF), regardless of the severity or relationship to study drug. The Investigator should treat patients with AEs appropriately and observe them at suitable intervals until the events stabilize or resolve. AEs may be discovered through observation or examination of the patient, questioning of the patient, complaint by the patient, or by abnormal clinical laboratory values.

In addition, AEs may also include laboratory values that become significantly out of range. In the event of an out-of-range value, the laboratory test should be repeated until it returns to normal or can be explained and the patient's safety is not at risk.

All adverse events should be recorded with causality assessment.

The information presented below is intended to provide issues to consider for adverse events associated with intrathecal injections of rhHNS. In general, these adverse events can be classified as follows:

- Adverse events due to systemic exposure to rhHNS caused by the drug diffusion from the CSF to the peripheral circulation;
- Adverse events related to the direct delivery of rhHNS to the intrathecal CSF space and meninges, and subsequent diffusion into brain parenchyma, via an intrathecal route
- IDDD-related adverse events.

Note: the classification of potential adverse events and the examples presented below are based on purely theoretical considerations and/or published literature as there is no human experience with intrathecal rhHNS therapy to date.

POTENTIAL ADVERSE EVENTS: INTRATHECAL RHHNS

Adverse Events Due To Systemic Exposure To rhHNS

Although rhHNS is given intrathecally only, some proportion of the drug will diffuse from the CSF into the peripheral circulation. The resulting systemic exposure may cause events that are typically seen in patients receiving ERT via an intravenous administration, known as infusion-related reactions. An infusion-related reaction is defined as an adverse event that (1) begins either during or within 24 hours after the start of the infusion, and (2) is judged as possibly or probably related to study drug. Other AEs that occur prior to the infusion, along with AEs associated with protocol-defined testing and assessments (laboratory testing and physical examinations) that were performed prior to the infusion will not be defined as infusion-related reactions.

Adverse Events Related to the Direct Delivery of rhHNS to the CNS Through Intrathecal Administration

Examples of adverse events observed in other published clinical trials with intrathecally-administered peptides or proteins, include, but are not limited to the following: headache, fever, feeling of warmth, sensory parathesias (including feelings of warmth, tingling, or pain) or autonomic symptoms such as dry mouth or gustatory abnormalities (including loss of smell and metallic taste). Changes in mental cognitive status or level of consciousness that are not caused by pre-medication may either occur acutely or develop post-injection, over time.

Potential Adverse Events: IDDD -Related Adverse Events

Examples of adverse events related to the insertion or use of an IDDD include, but are not limited to, the following: catheter disconnection or fracture, erosion of portal/catheter through the skin, fibrin sheath formation around catheter tip, hematoma, implant rejection, malposition of catheter, migration of portal/catheter, occlusion of portal/catheter, portal site or subcutaneous tract infection, and sepsis.

In addition, there are risks associated with intraspinal access, which include the following: cerebrospinal fluid leaks, dura mater or epidural vein perforation, epidural or intrathecal space infection (which could result in meningitis), inadvertent epidural placement, pain on injection, and spinal cord or nerve injury.

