7.21.2.2 Serious Adverse Event

A serious AE (SAE) is any AE occurring at any dose that results in any of the following outcomes:

- Death
- Is life-threatening
- Requires inpatient hospitalization
- Requires prolongation of existing hospitalization
- A persistent or significant disability or incapacity

- A congenital anomaly or birth defect

Important medical events that may not result in death, be life-threatening, or require hospitalization may be considered an SAE when, based upon appropriate medical judgment, they may jeopardize the patient and may require medical or surgical intervention to prevent one of the outcomes listed in this definition. Examples of such medical events include allergic bronchospasm requiring intensive treatment in an emergency room or at home, blood dyscrasias or convulsions that do not result in inpatient hospitalization.

The National Cancer Institute Common Terminology Criteria for Adverse Events (CTCAE) Version 3.0 grading scale should be referenced when assessing the severity of an AE (see [Appendix 5](#)) If an AE is not described in the NCI CTC, the severity should be recorded based on the scale provided in Table 7-4. The severity of all AEs/SAEs should be recorded on the appropriate eCRF page as Grade 1, 2, 3, 4, or 5 corresponding, respectively, to a severity of mild, moderate, severe, life-threatening, or death.

Table 7-4 Adverse Event Severity

Severity	Definition
Grade 1 (Mild)	No limitation of usual activities.
Grade 2 (Moderate)	Some limitation of usual activities.
Grade 3 (Severe)	Inability to carry out usual activities.
Grade 4 (Life-threatening)	Immediate risk of death.
Grade 5 (Death related to an AE)	Death

Relationship of an adverse event or serious adverse event to study medication is to be determined by the Investigator based on the definitions in Table 7-5:

Table 7-5 Adverse Event Relatedness

Relationship to Product(s)	Definition
Not Related	Unrelated to study drug.
Possibly Related	A clinical event or laboratory abnormality with a reasonable time sequence to administration of study drug, but which could also be explained by concurrent disease or other drugs or chemicals.

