Probably Related	A clinical event or laboratory abnormality with a reasonable time sequence to administration of study drug, unlikely to be attributable to concurrent disease or other drugs and chemicals and which follows a clinically reasonable response on de-challenge. The association of the clinical event or laboratory abnormality must also have some biologic plausibility, at least on theoretical grounds.
Definitely related	The event follows a reasonable temporal sequence from administration of the medication, follows a known or suspected response pattern to the medication, is confirmed by improvement upon stopping the medication (dechallenge) and reappears upon repeated exposure (rechallenge).

Table 7-5 Adverse Event Relatedness

Relationship to Product(s)	Definition
	Note that this is not to be construed as requiring re-exposure of the patient to study drug; however, the determination of definitely related can only be used when recurrence of event is observed.

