7.21.3 Procedures for Recording and Reporting Adverse Events

7.21.3.1 Reporting Serious Adverse Events

Any SAE, regardless of relationship to study medication, which occurs in a patient after informed consent, should be recorded by the clinical site on an SAE form. The SAE must be completely described on the patient's eCRF, including the judgment of the Investigator as to the relationship of the SAE to the study drug or device. The Investigator will promptly supply all information identified and requested by the Sponsor (or contract research organization [CRO]) regarding the SAE.

The Investigator must report the SAE to the Shire Pharmacovigilance and Risk Management Department AND to the Shire HGT Medical Monitor on an SAE form. This form must be completed and FAXED within 24 hours of the Investigator's learning of the event to:

Shire Pharmacovigilance and Risk Management Department:

International FAX: [REDACTED] (UK) OR **United States FAX:** [REDACTED]

AND

Shire HGT Medical Monitor: [REDACTED] MD

[REDACTED]
FAX: [REDACTED] (USA)

Any follow-up information must also be completed on an SAE form and faxed to the same numbers listed above.

In the event of a severe and unexpected, fatal, or life-threatening SAE, the clinical site must contact the Shire HGT Medical Monitor by telephone; this is in addition to completing and transmitting the SAE form as stated above. The following provides contact information for the Shire HGT Medical Monitor.

If an SAE is assessed as severe and unexpected, or life-threatening, contact:

[REDACTED] MD
[REDACTED]
Shire Human Genetic Therapies, Inc.
[name]
[name]
Telephone: [REDACTED]
Fax: [REDACTED] (USA)
Mobile: [REDACTED]

The Investigator must promptly report all required information to the Institutional Review Board (IRB)/ Independent Ethics Committee (IEC). It is the responsibility of the Sponsor to ensure that each Investigator receives a copy of any CIOMS I/ MedWatch report that has been submitted to the appropriate regulatory agencies notifying them of an unexpected related SAE. The Investigator or Sponsor must ensure that the IRB/IEC receives a copy of the report and that a copy is also filed within their study files.

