10.6 Efficacy, Safety, and Pharmacodynamic Evaluations

10.6.1 Primary Analyses

10.6.1.1 Safety Analysis

In general, safety assessments will be based on all assessments post-baseline. The assessment of safety will be based primarily on the frequency of treatment-emergent adverse events, due to study drug and on the frequency of clinically notable abnormal vital sign and laboratory values. Changes from baseline will be calculated by subtracting the baseline value from the post-baseline value.

All enrolled patients will be included in the safety analysis. Patients will be grouped according to the actual dose received.

No formal statistical test will be performed in the safety evaluations. Vital sign measurements, clinical chemistry, and hematology safety monitoring will be listed for each patient, and abnormal values will be flagged. These will also be summarized at each time point, including change from baseline.

Adverse events will be recorded throughout the study and at early termination. Adverse events and medical conditions will be coded using the Medical Dictionary for Regulatory Activities (MedDRA) Version 9.0 or later. In all cases (with the exception of device-related events), adverse event summaries will be based on all adverse event recorded beginning on Study Day 1 (treatment-emergent AEs).

Adverse events will be summarized by presenting, for each treatment group, the number and percentage of patients having any adverse event, having an adverse event in system organ class, and having each individual adverse event. Note that in any given category (eg, system organ class) a patient will only be counted once. In addition, those events which resulted in death or were otherwise classified as serious will be presented in a separate listing. The incidence of treatment-emergent adverse events (new or worsened from baseline) will be summarized by system organ class, severity, type of adverse event and relationship to trial medication.

Adverse events that occur up to 30 days after the last dose of study drug will be considered “on-treatment”. Adverse events which are deemed probably or possibly related to the device will be summarized by dose group and overall.

Laboratory data will be listed by patient and dose group. Patients with newly occurring abnormalities outside the normal range will be flagged and listed separately and summarized. Mean change from baseline values or shift tables will also be provided by dose group at each visit.

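### The infusion-related-reaction definition and the device-related adverse event summary name only two of the three related levels in Table 7-5 and leave out Definitely related

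*Protocol*

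**What the plan says.** Section 7.21.2.2 sets the causality scale. The relationship of an event "to study medication is to be determined by the Investigator based on the definitions in Table 7-5". That table has four levels: Not Related, Possibly Related, Probably Related and Definitely related. The last is a level of its own. It requires improvement when the drug is stopped and reappearance on repeated exposure, and a note adds that "the determination of definitely related can only be used when recurrence of event is observed".

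Two rules elsewhere select events by naming levels of such a scale:

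- Section 7.21.2.1, on adverse events from systemic exposure, defines an infusion-related reaction as one that begins during the infusion or within 24 hours of its start and "is judged as possibly or probably related to study drug".
- Section 10.6.1.1 states: "Adverse events which are deemed probably or possibly related to the device will be summarized by dose group and overall".

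On the device, Section 7.21.3.1 requires the record of a serious event to include "the judgment of the Investigator as to the relationship of the SAE to the study drug or device". No separate scale for device causality is given.

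The wording is the same in the original protocol (21 June 2010) and in Amendment 1 (27 January 2011).

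**The concern.** A rule that selects related events should admit every related level. These two admit the lower and middle levels and pass over the top one. Neither uses a phrase such as at least possibly, or simply related, that would bring the top level in. A programmer who codes the sentences as they stand would drop the events whose link to drug or device is best established.

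Dosing is repeated at 28-day or 14-day intervals, so recurrence of a reaction can be observed in the ordinary course of the study. Definitely related is therefore a level that investigators could actually use.

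Long-term safety is the primary objective and the implanted device is written into it. At most 12 patients are planned, over three dose groups, so one or two events placed in or out of a category can visibly change a group's count.

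**Working it through.** No figure in the protocol is at issue, so the check compares categories.

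**Related levels in Table 7-5:** Possibly, Probably, Definitely = 3.

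| Rule | Possibly | Probably | Definitely | Levels named |
|---|---|---|---|---|
| Infusion-related reaction, 7.21.2.1 | yes | yes | no | 2 of 3 |
| Device-related summary, 10.6.1.1 | yes | yes | no | 2 of 3 |
| Either rule after correction | yes | yes | yes | 3 of 3 |

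**Could Definitely be a subset of Probably?** No. Table 7-5 defines them in separate rows. Probably needs a reasonable response when the drug is withdrawn and biological plausibility. Definitely also needs recurrence. An event holds one grade, so naming Probably does not take in Definitely.

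**Where does a definitely related event still appear?**

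1. Section 10.6.1.1 summarises all treatment-emergent events by system organ class, "severity, type of adverse event and relationship to trial medication". No causality cut-off applies, so an event definitely related to the drug is counted and shown under its own level.
2. Serious events are listed separately, and all safety data are listed.
3. The relationship in item 1 is to trial medication. The device sentence is the only planned summary by relationship to the device. An event graded definitely device-related would be counted in the general tables if treatment-emergent, but no planned table would identify it as device-related.

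**Does any planned output use the infusion-related-reaction definition?** None does in Sections 10.1 to 10.6. That half is a faulty classification rule that a later count would inherit, not a fault in a stated table.

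**The case against.** The strongest reply is that this is a drafting slip with little consequence. Every adverse event is recorded whatever its relationship, with a causality grade. The main safety assessment rests on the frequency of treatment-emergent events and on notable vital-sign and laboratory values, and the overall event tables have no causality cut-off. The infusion-reaction definition sits in text offered as issues to consider and described as theoretical. The grouping could be put right at analysis. All of this stands. It limits the point to one summary table and one definition, but it does not make either rule correct.

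A second reply is that Table 7-5 is written for study drug. Its top level speaks of stopping and repeating the medication, so it may not carry over to a device. That also stands as a caveat, and the device half rests on assuming the same levels. The device rule does presuppose a graded scale, however, and on any scale with a definite level it leaves that level out.

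Three stronger readings are tempting, and the documents do not support them.

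- A reader might infer that a large share of a child's reactions would be lost. That needs a reaction rate per injection, which the protocol does not give. It also needs every repeat reaction to be graded definite, although Table 7-5 asks for more than recurrence. Nor would it be the statistic reported: Section 10.6.1.1 counts each patient once per category, so a child whose first reaction was graded possibly or probably related would still count as having one.
- A reader might infer that clear device failures, such as a fractured catheter or an infected port, would drop out of the device table. Under the recurrence note a first failure cannot be graded definite. It would be at most probably related, and so included. Only a repeat failure, for instance after re-implantation, could reach the omitted level.
- A reader might infer that the bias is greatest in Group 3 because it has the most injections. That rests on the same unsupported calculation of event shares.

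**Conclusion.** Wrong as written, and minor. Each rule admits two of three related levels. Followed literally, a definitely drug-related event falls outside the infusion-reaction definition, and a definitely device-related event falls outside the only planned summary by device relationship.

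The harm is misclassification and a possible undercount in the device summary, together with any later count that uses the infusion-reaction definition. No data are lost, and no magnitude can be derived from the documents.

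The conclusion rests on a literal reading of the two sentences and, for the device, on the Table 7-5 levels applying to it. It concerns the original protocol and Amendment 1. The cover lists amendments up to number 8, and later text or an analysis plan may have changed the wording.

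**What to change.** In Section 7.21.2.1, change the causality condition to 'possibly, probably or definitely related to study drug'. In Section 10.6.1.1, change the device sentence to 'possibly, probably or definitely related to the device'. In both places the intended set is any category other than Not Related, and defining it that way ensures that the top level cannot drop out.

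The cost is two wording changes. Data collection, dosing and clinical management are unaffected. The device count, and any infusion-reaction count made later, can only stay the same or rise.

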7.21.2.2 Serious Adverse Event

A serious AE (SAE) is any AE occurring at any dose that results in any of the following outcomes:

- Death
- Is life-threatening
- Requires inpatient hospitalization
- Requires prolongation of existing hospitalization
- A persistent or significant disability or incapacity

- A congenital anomaly or birth defect

Important medical events that may not result in death, be life-threatening, or require hospitalization may be considered an SAE when, based upon appropriate medical judgment, they may jeopardize the patient and may require medical or surgical intervention to prevent one of the outcomes listed in this definition. Examples of such medical events include allergic bronchospasm requiring intensive treatment in an emergency room or at home, blood dyscrasias or convulsions that do not result in inpatient hospitalization.

The National Cancer Institute Common Terminology Criteria for Adverse Events (CTCAE) Version 3.0 grading scale should be referenced when assessing the severity of an AE (see [Appendix 5](#)) If an AE is not described in the NCI CTC, the severity should be recorded based on the scale provided in Table 7-4. The severity of all AEs/SAEs should be recorded on the appropriate eCRF page as Grade 1, 2, 3, 4, or 5 corresponding, respectively, to a severity of mild, moderate, severe, life-threatening, or death.

Table 7-4 Adverse Event Severity

Severity	Definition
Grade 1 (Mild)	No limitation of usual activities.
Grade 2 (Moderate)	Some limitation of usual activities.
Grade 3 (Severe)	Inability to carry out usual activities.
Grade 4 (Life-threatening)	Immediate risk of death.
Grade 5 (Death related to an AE)	Death

Relationship of an adverse event or serious adverse event to study medication is to be determined by the Investigator based on the definitions in Table 7-5:

Table 7-5 Adverse Event Relatedness

Relationship to Product(s)	Definition
Not Related	Unrelated to study drug.
Possibly Related	A clinical event or laboratory abnormality with a reasonable time sequence to administration of study drug, but which could also be explained by concurrent disease or other drugs or chemicals.
Probably Related	A clinical event or laboratory abnormality with a reasonable time sequence to administration of study drug, unlikely to be attributable to concurrent disease or other drugs and chemicals and which follows a clinically reasonable response on de-challenge. The association of the clinical event or laboratory abnormality must also have some biologic plausibility, at least on theoretical grounds.
Definitely related	The event follows a reasonable temporal sequence from administration of the medication, follows a known or suspected response pattern to the medication, is confirmed by improvement upon stopping the medication (dechallenge) and reappears upon repeated exposure (rechallenge).

Table 7-5 Adverse Event Relatedness

Relationship to Product(s)	Definition
	Note that this is not to be construed as requiring re-exposure of the patient to study drug; however, the determination of definitely related can only be used when recurrence of event is observed.

